11.1. Primary Efficacy Endpoint Analysis

The primary efficacy endpoint for the study is the incidence of confirmed complete wound closure of the study ulcer, as assessed by the investigator, during the 12-week treatment phase, and confirm one week later.

The primary efficacy analysis will be conducted on the PEP. The proportion of subjects with confirmed closed ulcers during the Treatment Phase of the study, as assessed by the Investigator, will be compared using the Cochran–Mantel–Haenszel (CMH) test. For the primary efficacy analysis, missing values will be imputed using last observation carried forward.

The clinical study will be conducted under a common protocol for each investigational site with the intention of pooling the data for analysis. The Breslow-Day test will be used to assess the homogeneity of the primary endpoint across study sites. Sites with enrollment less than 6 will be combined to a new study site for testing. If the Breslow-Day test concludes lack of homogeneity (at a two-sided alpha level of 0.15), additional exploratory analyses will be performed to characterize the differences in results among sites.

A point estimate of the incidence will be presented along with its associated exact 95% confidence interval based on the binomial distribution for Active Treatment and Control Treatment patients respectively.

The complete wound closure as assessed by the Investigator will be listed for each patient.

In addition, subgroup analyses of the primary endpoint will be performed for age, sex, race, region, and other groupings if appropriate.

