## 8.12. Efficacy Analyses

### 8.12.1. Primary Analysis

Primary Endpoint: The primary analysis will be conducted on the ITT population. The proportion of subjects with confirmed closed study ulcers during the treatment phase of the study, as assessed by the investigator, will be compared using the *Cochran–Mantel–Haenszel (CMH)*. For the primary efficacy analysis, missing values will be imputed using last observation carried forward.

For the primary analysis, the first date of assessment of 100% re-epithelialization of the ulcer surface without detectable exudate will be used.

The Breslow-Day test will be used to assess the homogeneity of the primary endpoint across study sites. If the Breslow- Day test concludes lack of homogeneity

(at a two-sided alpha level of 0.10), additional exploratory analyses will be performed to characterize the differences in results among sites.

Secondary Endpoints: To maintain the trial-wise Type I error rate at 0.05, a closed test procedure will be used for the secondary endpoints. For efficacy analyses, the first date of assessment of 100% re-epithelialization of the ulcer surface without detectable exudate or visible non-epidermal tissue will be used.

The order of the endpoints will be as follows:

1. Proportion of subjects with confirmed complete wound closure of the study ulcer during the 12-week treatment phase as assessed by computerized planimetry, during the treatment phase
2. Time to complete wound closure, as assessed by the investigator.
3. Time to complete wound closure, as assessed by computerized planimetry.
4. Rate of ulcer closure as assessed by computerized planimetry.

Prognostic Factors Assessments: For the Intent-to-Treat population, a covariate analyses will be conducted to assess the impact of various prognostic factors on ulcer closure and also to demonstrate the robustness of the primary analysis. Prognostic factors (i.e., covariates) will be included if they are found to be contributing factors (i.e., the individual covariate p-value is less than 0.05). Potential prognostic factors to be considered include:

- Baseline ulcer size
- DM type
- Age of ulcer at baseline
- Race
- Gender
- Nicotine Use
- Recorded HbA1c
- Baseline BMI
- Ulcer location

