6. SAMPLE SIZE DETERMINATION AND RATIONALE

This is a randomized study with two treatment groups. Assuming:

- 46% of DFUs receiving PriMatrix close by 12 weeks (84 days).
- 26% of DFUs receiving with Standard of Care close by 12 weeks (84 days).

Overall 2-sided Type I Error rate (alpha) of 0.05. Under the above assumptions, 102 subjects per treatment group will be required to meet the Type I error rate of 0.05 and 80% power; for a total

of 204 subjects for the study. As the treatment duration is short, the discontinuation rate is predicted to be around 15%. To accommodate the potential discontinuations, 240 subjects will be randomized (120 per treatment group) to this trial. The subjects will be randomized to the treatment groups in a 1:1 ratio.

A single interim analysis when 50% of subjects complete the trial, using group-sequential methods and Pocock alpha spending function, where the hypotheses will be tested at a two-sided alpha of 0.031 at the interim analysis and at a two-sided alpha of 0.028 at the final analysis.

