7. RANDOMIZATION

The randomization will be stratified by center and will use mixed blocks of 2 and 4 with a 1:1 ratio to ensure even distributions of Active and Control subjects at each site. Trial ulcer size (area) at the time of randomization (2 strata: 1 cm² to ≤ 3 cm² vs. > 3 cm² to 12 cm²) will also be used as a stratification factor to ensure balance between treatment groups in this stratum.

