13.2. Methods of Analysis

13.2.1. Efficacy Endpoints

Confidence interval for proportions:

The method used to compute the two-sided 95% confidence interval (CI) for a single proportion will be the ‘exact’ method of Clopper and Pearson. For two proportions, the two-sided 95% CI for the proportion difference will be calculated based on the Z-test with continuity correction.

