13.2.3. Other Variables

Discontinuations

The difference between treatments, both overall and for each primary reason, will be compared by using a 2-sided Fisher's exact test.

Demographic and Baseline Characteristics

Comparisons between treatment groups of continuous variables will be made by using a one-way analysis of variance with treatment as a factor. For categorical variables, the Fisher's exact test will be used. All tests will be 2-sided and performed at the 0.05 level of significance.

Time-to-Event Data

Time-to-event endpoints including time-to-complete-wound-closure/healed will be evaluated using the Kaplan-Meier method. The log-rank test will be used to compare the distributions between two treatment groups, stratified by the ulcer size (1 cm² to ≤ 3 cm² vs. > 3 cm² to 12 cm²).

Rate of Wound Closure, as Assessed by Computerized planimetry

Analysis of Covariance (ANCOVA) will be used to compare the rate of wound closure (as defined in section 13.2.2 for the two treatment groups. The stratification factor, ulcer size at the time of randomization, will be used in this analysis. Other covariate, as outlined in section 11.4, may also be incorporated in the model, if their presence is statistically significant (i.e. p-value ≤ 0.05).

Safety Data

The primary safety endpoint for this study is any severe device-related complication where relationship to the device was assessed by the clinical event committee possible, probably, or definite. Fisher's exact test will be used to compare incidence rates of serious device-related complications as well as for any device-related complication, and for specific complications between the treatment group and the control group.

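### The primary CMH test names no strata and its interval is unstratified, although randomisation is stratified by centre and ulcer size

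*SAP*

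**What the plan says.** **Primary test.** SAP 11.1 states that the proportions with confirmed closure "will be compared using the Cochran–Mantel–Haenszel (CMH) test". Protocol 8.12.1 ("The proportion of subjects with confirmed closed study ulcers during the treatment phase of the study, as assessed by the investigator, will be compared using", where CMH is the method named) and the synopsis have the same plan. None of the three names a stratification variable.

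**Randomisation.** SAP 7: "The randomization will be stratified by center and will use mixed blocks of 2 and 4". It then adds ulcer area in two classes, 1 to 3 cm² and above 3 to 12 cm². The measure is "Trial ulcer size (area) at the time of randomization", and the SAP says that it "will also be used as a stratification factor to ensure balance between treatment groups in this stratum". Protocol 8.4 agrees.

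**Interval for the difference.** SAP 13.2.1 has it "calculated based on the Z-test with continuity correction", with no strata.

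**Factors named for other analyses.**
- SAP 13.2.3: the log-rank test is "stratified by the ulcer size", and the ANCOVA of closure rate also uses ulcer size only.
- SAP 11.4 and protocol 8.12.1: the ANCOVA of ulcer-size reduction uses site and baseline ulcer area.
- Protocol synopsis: the logistic regression for planimetric closure uses the stratification factors, without listing them.
- SAP 11.1: Breslow-Day homogeneity is tested across sites, with sites that enrolled fewer than 6 combined. Whether that pooling also applies to the CMH test is not said.

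**The concern.** A CMH test is defined by its strata. Without them it reduces to a single-table chi-square test that makes no use of the factors by which subjects were randomised. Since the other analyses use different factors, a programmer could defend no strata, ulcer size, pooled site, pooled site by size, or full site by size. These give different p-values for the same data.

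The interval is a separate matter, because here the SAP is explicit: it is unstratified and continuity-corrected. It can therefore disagree with a stratified primary test, and it is wider than it needs to be.

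The choice should be closed in writing. The trial is open-label, and SAP version 1.0 is dated 03 August 2020, after the 21 May 2020 date that fixed the primary analysis set (SAP 10.4).

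**Working it through.** **1. The plan's own figures.** Inputs from SAP 6 and 9.1: 46% vs 26%, 102 per arm, two-sided 0.031 at half information and 0.028 at the end.
- Pooled variance at the mean rate of 0.36: SE = √(2 × 0.36 × 0.64 / n).
- Interim, n = 51: SE 0.0951, drift 0.2/0.0951 = 2.104, critical value 2.157. P(stop for superiority) = 1 − Φ(2.157 − 2.104) = 0.479, as stated.
- Both looks together (bivariate normal, correlation √0.5): power 0.803, against the stated 80%.

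The design figures reproduce. They come from an unstratified two-proportion calculation, so they do not settle which strata the test uses.

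**2. One data set, two readings.** The counts are assumed, with 207 subjects as in SAP 11.1.1. The statistic is (Σ(a − E))² / ΣV, with E = n₁m/n and V = n₁n₀m(n − m)/(n²(n − 1)), without continuity correction.
- No strata, 42/104 vs 27/103: E = 34.667, V = 11.556. χ² = 7.333²/11.556 = 4.654, p = 0.0310. This fails 0.028.
- By size, small 27/52 vs 18/52 (E 22.5, V 6.444) and large 15/52 vs 9/51 (E 12.117, V 4.647): χ² = 7.383²/11.091 = 4.915, p = 0.0266. This passes.

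**3. The interval on the same data.**
- As stated in the SAP (usual correction assumed): difference 0.1417, SE 0.0648. Half-width = 1.96 × 0.0648 + ½(1/104 + 1/103) = 0.1269 + 0.0097 = 0.1366.
- Mantel-Haenszel by size: difference 0.1427, SE 0.0633. Half-width = 1.96 × 0.0633 = 0.1240.
- Ratio 0.1366/0.1240 = 1.10. Most of the excess is the continuity correction (0.0097/0.1269 = 7.6%). Ignoring size adds about 2% (0.1269/0.1240).

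**4. How often it matters.** Simulation of 207 subjects at the final look only (level 0.028), with permuted blocks of 2 and 4 within site by size. Assumptions that the documents do not give: 15 or 30 sites of uneven size (the protocol says up to 30), between-site SD 0.3 to 0.8 on the logit scale, 40% large ulcers, size log-odds effect 1.0.
- At 46% vs 26%, the five readings do not all agree in about 6% to 10% of trials.
- At 41% vs 26%, in a run with 30 sites and half the ulcers large, they disagree in about 14%.
- No strata vs size alone: about 2% to 4%. In runs that varied the size odds ratio from 1 to 3, it was 0.4% to 2.2%.
- No true difference, 30 sites: each single reading rejects in 2.2% to 3.0% of trials. At least one of five rejects in 3.8% to 4.2%.
- The stated interval averages about 9% wider than Mantel-Haenszel by size. Its coverage is about 97%, against about 95% to 96%. It disagrees with the size-stratified test at 0.05 in about 4% to 5% of trials.

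Power (%) at 46% vs 26%, 2,500 trials per row:

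| Site SD, sites | None | Size | Pooled site × size | Full site × size |
|---|---|---|---|---|
| 0.3, 30 | 80.4 | 81.2 | 80.9 | 78.6 |
| 0.8, 30 | 80.5 | 81.5 | 84.0 | 82.2 |
| 0.8, 15 | 79.6 | 81.1 | 83.3 | 82.9 |

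Monte Carlo error on a disagreement rate of 8% is about √(0.08 × 0.92/2500) = 0.5 points.

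**The case against.** The strongest reply is that little turns on this. Each reading is a sound test. No strata and size alone rarely give different verdicts, and their power differs by only 1 to 2 points. Much of the disagreement comes from the full site-by-size reading, with up to 60 cells for 207 subjects (about 3.5 each), which the SAP never proposes. The Breslow-Day test across sites, with small sites pooled, could be taken to imply a CMH test by pooled site. SAP 11.4 also plans a covariate analysis that includes baseline ulcer size.

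Most of this stands, and it limits the size of the point. It does not remove it. The pooling sentence is tied to the homogeneity test, and the covariate analysis is a robustness check in the ITT population that does not define the primary test. Nor do the documents dictate ulcer size alone, since centre is also a randomisation factor and two other planned analyses go beyond size.

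Three stronger readings might be inferred, and none is supported:
- **That the type I error is inflated.** Any one reading stays close to 0.028. The 3.8% to 4.2% arises only if the best of five is picked.
- **That full site-by-size stratification loses power.** It does at a site SD of 0.3 with 30 sites. At 0.8 it has more power than no strata and than size alone.
- **That the strata were, or will be, chosen after seeing results.** The dates make a written record important, but nothing in the documents says that this happened.

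**Conclusion.** The point holds as a gap in specification together with an inefficient stated interval. Taken literally, the primary test and its interval ignore the randomisation strata, and the other planned analyses conflict too much to fill the gap. The open choice can decide the result only when the p-value lies near 0.028. The disagreement rates depend on site numbers, site variation, ulcer mix and size effect, none of which the documents give beyond a maximum of 30 sites. Two findings are firmer: size strata gave slightly more power than none in every scenario tabulated, and the continuity-corrected interval is conservative. No single set of strata is best under all assumptions. Size alone leads at low site variation, and pooled site by size leads at high site variation. This should be corrected, but it does not invalidate the trial.

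**What to change.** - **SAP 11.1:** stratify the CMH test by the randomisation ulcer-size class (1 to 3 vs above 3 to 12 cm²), in line with the log-rank test and the closure-rate ANCOVA. Make pooled site by size the sensitivity analysis, and say that the rule combining sites under 6 applies to it. The reverse order is equally acceptable, provided that one is named as primary.
- **SAP 13.2.1:** replace the continuity-corrected Z interval for the difference with the Mantel-Haenszel risk difference and its interval, over the same strata as the primary test.
- **Record:** state the date of the choice and that it preceded any review of outcomes by arm. If that cannot be stated, say so and report both analyses side by side.

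The cost is a few sentences in the SAP and minor programming. No new data are needed.

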#### 5.18. Investigator Assessments of Ulcer Closure

**Complete wound closure** is defined as 100% re-epithelialization of the ulcer surface without detectable exudate, confirmed on 2 consecutive study visits 1 week apart (i.e., Treatment Visit where 100% re-epithelialization of the ulcer surface without detectable exudate was initially documented and the Closure Confirmation Visit). For efficacy analyses, the first date of assessment of 100% re-epithelialization of the ulcer surface without detectable exudate will be used as the date of closure.

If, at Treatment Week 12, the ulcer remains open, the investigator will document why, in his opinion, the ulcer did not close.

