### 8.10.2. Per Protocol Population

The Per Protocol (PP) population is defined as all randomized subjects who were not associated with a major protocol violation. This population will be identified before the database lock. The PP analysis of primary and secondary endpoints will be considered supportive.

For the per protocol analysis, no data points will be imputed, all missing values will remain as missing.

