### 8.12.6. Supportive Analysis

To assess the robustness of the primary analysis results, supportive analysis will be conducted using the PP population. Statistical methodology for the supportive analyses will be the same as that of the primary analysis, with the exception of the analysis population used. The PP population will be used for the supportive analysis while ITT population will be used for the primary analysis. Subjects in these populations with no post randomization data for the primary endpoint will be considered NOT CLOSED, i.e., treatment failures, in this analysis.

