11.6. Missing Data

For efficacy evaluation data points, the last available observation (LOCF) will be used. In the analyses using the planimetry data, the last available planimetric value will be used for discontinued subjects. All subjects discontinued during the treatment period and before 100% wound closure during the treatment phase of the study will not be replaced and will be considered treatment failures for the primary and secondary endpoints evaluations.

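### LOCF in the binary primary analysis can count an unconfirmed closure as a success against the endpoint definition, and no order of precedence is stated

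*SAP*

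**What the plan says.** **Definition.** Complete wound closure must be "confirmed on 2 consecutive study visits 1 week apart" (protocol 5.18; the SAP list of abbreviations agrees). The proportion tested in SAP 11.1 is that of subjects with confirmed closure.

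**LOCF.** For the primary efficacy analysis, SAP 11.1 and protocol 8.12.1 both state that "missing values will be imputed using last observation carried forward". SAP 11.6 extends LOCF to efficacy data points in general. Protocol 8.12.3 ties its own LOCF sentence to continuous analyses and planimetry.

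**Failure.** SAP 11.5 and protocol 8.12.3 make a failure of anyone who withdraws during the treatment phase and/or does not reach complete wound closure. SAP 11.6 is narrower: "All subjects discontinued during the treatment period and before 100% wound closure during the treatment phase of the study will not be replaced", and those subjects are the failures. Protocol section 7 has a similar narrow form. Neither narrow form mentions confirmation.

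**PP analysis.** Protocol 8.10.2: "For the per protocol analysis, no data points will be imputed, all missing values will remain as missing". Protocol 8.12.6: "Subjects in these populations with no post randomization data for the primary endpoint will be considered NOT CLOSED", with otherwise the same method as the primary analysis. SAP 12.8 also takes the primary method and changes only the population. SAP 10.2 neither repeats nor withdraws the no-imputation sentence.

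**The concern.** Neither document says what LOCF carries forward (the closed/open status at the last visit, or the confirmed status), or which rule wins when LOCF and the failure rule disagree. A programmer could follow SAP 11.1 and 11.6 to the letter and score an unconfirmed closure as a success. Another could follow the definition and SAP 11.5 and score it as a failure.

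The confirmation requirement guards against a single mistaken or transient closure. It matters more here because the assessing investigator knows the treatment (protocol 8.5, SAP 8). If the choice is left until the data are in hand, it can be made knowing which reading gives the better result.

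The PP conflict is a separate and smaller matter: a supportive analysis meant to show robustness has no single stated missing-data rule.

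**Working it through.** **1. Where the rules differ.**

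| Last information on the subject | Definition and SAP 11.5 | Failure sentence of SAP 11.6 | LOCF of visit-level status |
|---|---|---|---|
| Open, then lost | Failure | Failure | Open, so failure |
| Closed once, no Confirmation Visit | Failure | Not reached | Closed, so success |
| Closed and confirmed | Success | Not reached | Success |

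Only the second row differs. If LOCF carries confirmed status instead, that row is a failure too, and LOCF does nothing in this binary analysis. LOCF is therefore either redundant or contrary to the definition.

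**2. The plan's own figure.** Inputs from SAP 6: 46% vs 26%, overall two-sided alpha 0.05, one look at 50% tested at 0.031, final test at 0.028, 102 per arm for 80% power. With pooled variance (mean rate 0.36), the drift is 0.20 / √(2 × 0.36 × 0.64 / 102) = 2.976. At half the information it is 2.976 × √0.5 = 2.104. The 0.031 bound is z = 2.157, so the probability of stopping early for superiority is Φ(2.104 − 2.157) = 0.479, as SAP 9.1 states. Two-look power is 0.803 at 102 per arm and 0.799 at 101. The design figures reproduce, and this point does not change them.

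**3. Size of the ambiguity (illustration).** SAP 11.1.1 gives 207 subjects in the primary efficacy population (PEP) without a split by arm; 104 Active and 103 SOC are assumed. At the planned rates, 0.46 × 104 = 47.8 and 0.26 × 103 = 26.8, so 48 and 27 closures. These are treated as the counts when unconfirmed closures score as successes. The test is

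z = (a/104 − c/103) / √[P(1 − P)(1/104 + 1/103)], with P = (a + c)/207,

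used as an unstratified stand-in for CMH.

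| Unconfirmed, Active / SOC | Counts under the failure rule | z | Two-sided p |
|---|---|---|---|
| 0 / 0 | 48/104 vs 27/103 | 2.984 | 0.0028 |
| 5 / 0 | 43/104 vs 27/103 | 2.301 | 0.021 |
| 6 / 0 | 42/104 vs 27/103 | 2.163 | 0.031 |
| 8 / 0 | 40/104 vs 27/103 | 1.883 | 0.060 |
| 5 / 3 | 43/104 vs 24/103 | 2.774 | 0.0055 |
| 0 / 5 | 48/104 vs 22/103 | 3.770 | 0.0002 |

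Single-stratum CMH gives nearly the same values (0.0029, 0.0217 and 0.0310 for the first three rows). Six subjects are 6/207 = 2.9% of the PEP. With the split reversed, the planned rates give 47/103 vs 27/104 (p = 0.003). Five Active reclassifications give 42/103 (p = 0.024) and six give 41/103 (p = 0.034), so the threshold is again six.

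**4. PP analysis.** Leaving values missing drops subjects from the denominator. Failure imputation keeps them. LOCF keeps them as well, because closure status is assessed at TV1 (protocol Table 3), so an open status is always available to carry. The three rules therefore give at most two denominators.

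**The case against.** The strongest reply is that the documents already settle the matter as failure. SAP 11.5 fails anyone without complete wound closure, and that defined term includes confirmation. Protocol 3.2.2 and SAP 4 call only confirmed closures successes. SAP 13.2.2 dates closure from the first of two successive assessments. Protocol 8.12.3 places LOCF with continuous data. Much of this stands: failure is the better-supported reading, and the fix follows it. It does not dispose of the point, because SAP 11.1 and protocol 8.12.1 apply LOCF to the primary closure analysis by name and give no precedence.

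A reader might also infer more than the documents support:

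- *That one unconfirmed closure could decide the trial.* Under the assumed split, 43/104 vs 27/103 passes 0.028 and 42/104 does not. Any threshold has such a pair, and this one depends on the split: 42/103 vs 27/104 gives p = 0.024 and passes.
- *That leaving values missing affects the primary analysis.* That rule appears only in protocol 8.10.2, for the PP analysis.
- *That the PP result could move from 46% to 39%.* This takes 15% missing (0.46 × 0.85 = 0.391), but SAP 10.4 says the expected 15% loss to follow-up did not occur. SOC would also move, from 26% to 22% (0.26 × 0.85 = 0.221), so the difference would go from 20 to 17 points. This does not show that the PP analysis is worthless.
- *That the 21 May 2020 date cuts off confirmations.* It is 79 days after 3 March 2020, short of day 84, but SAP 11.1.1 indicates that the analysis waits for 12 weeks of treatment and follow-up.

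**Conclusion.** The point holds in a limited form. The primary analysis has two stated rules that disagree for one kind of subject, closed once and never confirmed, and nothing says which governs. Applied to visit-level status, LOCF would credit a success that the definition denies.

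The effect on the result depends on imbalance between arms. From the planned rates it takes six unconfirmed closures, all in the Active arm, to move p from 0.003 to 0.031 and past 0.028. Losses of five Active and three SOC leave p at 0.006. These values rest on an assumed 104/103 split, assumed closure counts and an unstratified test. The documents report no unconfirmed closures, so they do not show that the outcome turns on this.

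The PP rules in protocol 8.10.2 and 8.12.6 and SAP 12.8 do conflict, but only for a supportive analysis. This is a specification gap that should be closed before database lock, not evidence of a biased result.

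**What to change.** - In SAP 11.1 and 11.6 and protocol 8.12.1, remove LOCF for the binary closure endpoints. State that a subject without closure documented at both the first closure visit and the Confirmation Visit is a failure, including when first closure is at TV13 and confirmation falls after it. SAP 11.5 and the definition already imply this.
- Keep LOCF, if at all, for continuous area data, as in protocol 8.12.3.
- Reconcile protocol 8.10.2 with protocol 8.12.6 and SAP 12.8, so that the PP analysis uses the same rule as the primary one.
- Add a sensitivity analysis that counts unconfirmed closures as successes, and report their number by arm.

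The cost is wording in both documents and one extra table. Closure rates may fall slightly compared with a LOCF reading. The sample size is unaffected.
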